7.3.2. Missing Data

In general, there will be no substitutions made to accommodate missing data points. All data recorded on the case report form (CRF) will be included in data listings that will accompany the clinical study report.

7.3.2.1. Handling of Missing Date Values

Partial or Missing Dates

The following conventions will be used to impute missing portions of dates for adverse events and concomitant medications, if warranted. Note that the imputed values outlined here may not always provide the most conservative date. In those circumstances, the imputed value may be replaced by a date that will lead to a more conservative analysis.

A. Start Dates

- 1) If the year is unknown, then the date will not be imputed and will be assigned a missing value.
- 2) If the month is unknown, then:
 - i) If the year matches the first dose date year, then impute the month and day of the first dose date.

- ii) Otherwise, assign 'January.'
- 3) If the day is unknown, then:
 - i) If the month and year match the first dose date month and year, then impute the day of the first dose date.
 - ii) Otherwise, assign the first day of the month.
- B. Stop Dates
 - 1) If the year is unknown, then the date will not be imputed and will be assigned a missing value.
 - 2) If the month is unknown, then assign 'December.'
 - 3) If the day is unknown, then assign the last day of the month.

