8.5. Prior and Concurrent Medications

The number and percentages of all concomitant medications will be summarized by treatment group, Anatomical Therapeutic Chemical (ATC) level 4 and PT. The total number of concomitant medications and the number and percentages of subjects with at least 1 concomitant medication will be summarized by treatment group. All summaries will be performed using the safety population.

The number and percentages of all prior medications will be summarized similarly to concomitant medications in a separate table.

A concomitant medication is defined as any medication taken on or after the day of first dose of study drug. The prior medications are defined as any medication that starts and ends prior to the first dose of study drug.

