10.1. Adverse Events

The number and percent of subjects with any treatment-emergent adverse events (TEAEs) will be displayed by system organ class and preferred term (MedDRA Version 18.0) for each treatment group. Within each preferred term, subjects will be counted only once if they had more than one event reported during the treatment period.

TEAEs will also be summarized by greatest reported severity for each event preferred term. Counts indicate subjects reporting one or more TEAEs that map to the severity grade classification for each preferred term. At each level of summarization (system organ class or event preferred term) subjects are only counted once and the worst severity case of repeated instances of the same TEAE will be used in tabulations. TEAEs will also be summarized by strongest investigator assessment of relationship to study drug in a similar manner.

Analyses of AEs will be performed for those events that are considered treatment emergent, where treatment emergent is defined as any AE with onset or worsening on or after the first dose of study drug up until 30 days after the last dose of study drug.

Treatment emergent summarization will be characterized by serious or not, the severity and the relationship with the study drug. A conservative approach will be taken to assess the relationship of an AE to study drug; if the relationship of an event is missing, it will be considered treatment-related. Missing severity will be coded as severe.

All TEAEs will be listed individually by subject. In addition, a separate listing will be produced for AEs that are not treatment-emergent.

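### SAP 7.3.2.1 imputes the first-dose date for a partial start date without checking the stop date, so an adverse event known to have ended before dosing can be classed as treatment-emergent

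*SAP*

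**What the plan says.** SAP 7.3.2.1 gives conventions to "impute missing portions of dates for adverse events and concomitant medications, if warranted". Two start-date branches use the first dose:

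- A.2.i, month unknown: "If the year matches the first dose date year, then impute the month and day of the first dose date".
- A.3.i, day unknown: "If the month and year match the first dose date month and year, then impute the day of the first dose date".

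The stop-date rules stand apart from these. For a missing day, B.3 reads: "If the day is unknown, then assign the last day of the month". It refers neither to the start date nor to the first dose. The introduction to the section adds that, where an imputed date is not the most conservative one, "the imputed value may be replaced by a date that will lead to a more conservative analysis".

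Two definitions use the resulting dates. In SAP 10.1, "treatment emergent is defined as any AE with onset or worsening on or after the first dose of study drug", with an upper limit of 30 days after the last dose. In SAP 8.5, "The prior medications are defined as any medication that starts and ends prior to the first dose of study drug"; a concomitant medication is one taken on or after the day of first dose.

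**The concern.** Setting an unknown start to the first dose is a sensible cautious default when it is unclear whether something began before or after dosing. It is not sensible when the recorded stop date already settles the matter. Branches A.2.i and A.3.i do not make that distinction, so they can produce a record that starts after it ends, and the SAP definitions then classify the record by that impossible start.

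This trial can be expected to collect the relevant kinds of record. Adverse events are reported from informed consent (Protocol 9.7.3). Subjects withdraw anti-spasticity drugs during a washout of up to 21 days before randomization, and all medications taken in the 90 days before baseline are recorded (Protocol 7.7). Events during withdrawal of the old treatment could therefore enter the TEAE tables of any arm, placebo included. Records of stopped drugs could leave the prior-medication table.

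**Working it through.** No figure in the plan is to be reproduced. The check applies the start-date and stop-date rules of SAP 7.3.2.1 literally to illustrative dates, then classifies the result with SAP 10.1 and 8.5.

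**Example 1, adverse event, day missing (A.3.i).** Start on an unknown day in March 2018, known stop 12 March 2018, first dose 20 March 2018. Month and year match, so the imputed start is 20 March. Start minus stop = 20 − 12 = 8 days, an inverted record. The onset is on the day of first dose, so the event satisfies "any AE with onset or worsening on or after the first dose of study drug" although it ended 8 days before dosing.

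**Example 2, medication, month missing (A.2.i).** Start recorded only as 2018, known stop 18 September 2018, first dose 2 October 2018. The year matches, so the imputed start is 2 October, 14 days after the stop (12 days to 30 September plus 2). The start is not before first dose, so the record is not prior. By its recorded stop, it was not taken on or after first dose either, so it does not meet the concomitant definition on that basis. Depending on which date the program uses, the drug goes into the concomitant table or into neither table.

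**Example 3, timing truly unknown.** Start and stop both on unknown days in March 2018, first dose 20 March. Imputed start 20 March, imputed stop 31 March. There is no inversion, and treatment-emergent status is a fair cautious default.

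**How often the rule misfires among eligible records.** Take adverse events that begin and end within the washout, with a known stop and a partial start. Every first-dose date in one calendar year and every start/stop pair inside the washout was enumerated, all treated as equally likely (an assumption).

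| Washout | Day missing (A.3.i): inverted and TEAE | Month missing (A.2.i): inverted and TEAE |
|---|---|---|
| 7 days | 84% | 99% |
| 14 days | 68% | 97% |
| 21 days | 53% | 96% |

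Under A.3.i the misfire occurs exactly when the event starts in the calendar month of the first dose, which is why the share falls as the washout lengthens. These are shares of partial-date records of this kind, not of all adverse events.

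**Which branch reaches long-standing anti-spasticity drugs.** Inclusion criterion 6 requires a regimen stable for at least 3 months before baseline. With starts 90 to 365 days before first dose (276 start days × 365 first-dose dates = 100,740 combinations), A.3.i applied in none. A.2.i gave an inverted date in 38%, namely those starting in the same calendar year as the first dose. Starts in an earlier year go to January under A.2.ii and are unaffected.

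**The case against.** The strongest reply is that the section already leaves room to avoid the error. The conventions apply only if warranted, SAP 7.3.2 sets a general default of no substitution, and an imputed date may be replaced by a more conservative one. So it would be wrong to infer that such a record is always set to the first-dose date. That much stands. But none of these clauses requires a look at the stop date, and for adverse events a more conservative date would tend to keep treatment-emergent status.

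A second reply is that first-dose imputation is a deliberate convention, in line with treating missing causality as related and missing severity as severe (SAP 7.3.2.2). This is right where timing is unknown, as in Example 3. It does not extend to records whose stop date shows that they ended before dosing.

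Three stronger readings are tempting, and the documents do not support them:

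- *Properly washed-out drugs will be tabulated as concomitant.* The SAP's own definition asks whether the drug was taken on or after the first-dose day, and a drug stopped earlier was not. What follows from the text is only that the record no longer meets the definition of prior.
- *Subjects could be lost from the per-protocol set.* SAP 8.2 bases exclusion on a blinded sponsor review of the data, and SAP 7.3.7 describes SDTM as holding observed data. Nothing says that imputed dates feed that review.
- *A number of affected subjects can be given.* The documents contain no frequency of partial dates, so any count would be a guess.

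**Conclusion.** The point holds as a limited defect in a stated rule. Read literally, A.2.i and A.3.i give a start after the stop for an adverse event with a partial start and a known pre-dose end, and SAP 10.1 then counts it as treatment-emergent. For medications, A.2.i can give an inverted date that removes the record from the prior category; its placement after that is a programming matter.

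The size is modest. The affected outputs are the TEAE and medication tables. These are descriptive, and Protocol 11.5 plans no statistical tests for safety. The mechanism does not depend on treatment arm, so the expected result is some over-counting in all arms and not a bias for or against AERT. No effect on the co-primary analyses or the per-protocol set is shown. The percentages in the working rest on equally likely dates and apply only to records that already have a partial start and a known pre-dose stop; how many of those will occur is unknown.

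**What to change.** Add to SAP 7.3.2.1 A:

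> If the known stop date, or the known parts of a partial stop date, show that the event or medication ended before the first dose, do not impute the first-dose date. Assign the earliest date compatible with the known parts of the start date (1 January, or the first day of the known month), never later than the stop date. Such events are not treatment-emergent and such medications are prior.

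The first-dose default stays where the stop date is missing or could be on or after first dose.

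In Example 1 the start becomes 1 March 2018 and the event is not a TEAE. In Example 2 it becomes 1 January 2018 and the drug is prior. Example 3 is unchanged.

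The cost is a short SAP addition and one condition in the date-imputation code, made before unblinding. No new data are needed.

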7.3.2.2. Imputation Methods

Observed cases, without imputation, will be used for the majority of analyses. A modified worst observation carried forward (mWOCF) imputation method will be utilized in a sensitivity analysis for the co-primary efficacy endpoints. For mWOCF imputed data, subjects who withdraw from the trial early due to an AE will have their missing data imputed using WOCF; all other missing data will be imputed using the last observation carried forward (LOCF).

If the relationship of an AE is missing, it will be considered treatment-related. Missing AE severity will be coded as severe.

7.3.3. Handling of Early Termination Visit Information

If a subject is terminated early from this study the early termination visit data will be analyzed at the closest scheduled visit. If the closest visit has valid data, the early termination data will be assigned to the next available visit.

7.3.4. Pooling of Study Centers

Study center will be included as an effect in the efficacy analyses. If necessary, study centers may be pooled prior to analyses. This pooling will take place and be documented prior to unblinding.

7.3.5. Coding Conventions for Events and Medications

All adverse events, and medical history will be mapped to the Medical Dictionary for Regulatory Activities (MedDRA Version 18.0) system for reporting (preferred term and body system).

Prior and Concomitant medications will be coded using WHO-DD (Drug Dictionary) (Version June 2015).

7.3.6. Analysis Software

[figure not shown]
Data manipulation, tabulation of descriptive statistics, calculation of inferential statistics, and graphical representations will be performed primarily using SAS (release 9.4 or higher) for Windows. If the use of other software is warranted, the final clinical study report will detail what software was used and for what purposes.

7.3.7. Study Data

All study data will be formulated into regulatory compliant data sets to provide transparency, traceability, and integrity of trial analysis results from the collection source. Observed study data will be mapped to the CDISC Study Data Tabulation Model (SDTM) and serve as the source data from the trial. All study analyses will be completed using analysis data sets that are derived from the SDTM and follow the CDISC Analysis Data Model (ADaM) architecture. All planned analyses will be performed using the ADaM data sets developed for this study.

The methods for programming the CDISC SDTM and ADaM data sets are described in Figure 2.

Figure 2 SDTM, ADaM, and TFL Development and Validation

Where:

1. Development, Validation, and Maintenance of SDTM Domains

2. Development and Validation of Analysis Data Sets (ADaM), with input source the appropriate SDTM domains.
3. Development and Validation of Tables, Figures, and Listings (TFL), with input data source the analysis specific ADaM data sets.

7.4. Planned Study Analyses

7.4.1. Statistical Summaries: Descriptive and Inferential

All statistical tests will be two-sided and a difference resulting in a p-value of less than or equal to 0.05 will be considered statistically significant. All p-values will be rounded to and displayed in four decimals. If a p-value less than 0.0001 occurs it will be shown in tables as <0.0001.

Descriptive summaries of variables will be provided where appropriate. For continuous variables, the number of non-missing values (n) and the median, mean, standard deviation, minimum, and maximum will be tabulated by treatment. For categorical variables, the counts and proportions of each value will be tabulated by treatment. Expansion of descriptive table categories within each treatment may occur if such elaborations are thought to be useful.

For the summary statistics of all numerical variables unless otherwise specified, minimum and maximum will be displayed to the same level of precision as reported. Mean and median will be displayed to one level of precision greater than the data collected. The standard deviation / standard error will be displayed to two levels of precision greater than the data collected.

Change from baseline scores will be calculated as the post-baseline measurement minus the baseline value.

All collected data will be presented in listings. Data not subject to analysis according to this plan will not appear in any tables or figures but will be included in the data listings.

7.4.2. Interim Analyses and Data Monitoring

No formal interim analysis is planned for this study. The Data Safety Monitoring Board (DSMB) may request safety information at its discretion at any time during the study. Further details of the DSMB can be found in the DSMB Charter.

7.5. Multiple Testing Procedures

The AERT 40 mg dose will be compared with placebo first (for both TNmAS-MAL and CGIC). If both comparisons are significant (showing superiority) at the 0.05 level then the AERT 80 mg dose will be tested at the 0.05 level (both TNmAS-MAL and CGIC). Both co-primary efficacy endpoints need to meet the 0.05 level for the AERT 40 mg dose comparison with placebo for the study to be considered a success. Therefore, no adjustment for multiplicity is needed. No other adjustments for multiplicity will be implemented.

8. SUMMARY OF STUDY DATA

8.1. Subject Disposition

A summary of the analysis sets includes the number and percentage of subjects in each treatment group for the following categories: subjects screened, subjects randomized, subjects in the safety population, subjects in the ITT population, subjects in the mITT population, and subjects in the PP population. All percentages will be based on the number of subjects randomized.

End of trial information will also be summarized in this table, including the number of subjects completing the study and the number of subjects who prematurely discontinued the study with reasons for withdrawal. All percentages will be based on the number of subjects randomized.

A by-subject data listing of study completion information including the reason for premature study withdrawal, if applicable, will be presented.

8.2. Protocol Deviations

Major protocol violations, as determined by a Sponsor blinded review of the data prior to database lock and unblinding of the study, may result in the removal of a subject's data from the PP population. The Sponsor or designee will be responsible for producing the final violation file; this file will include a description of the protocol violation and clearly identify whether or not this violation warrants exclusion from the PP population. This file will be finalized prior to database lock, and all information will be included in the SDTM.DV domain (deviations domain).

All protocol violations will be presented in a data listing, with a flag to indicate if a violation was considered major and resulted in the exclusion of the subject from the PP population. A summary table will be generated based on the classification of protocol deviations.

8.3. Demographics and Baseline Characteristics

Subject demographic data and baseline characteristics will be tabulated and summarized descriptively by treatment group and overall. The demographic data and baseline characteristics will be summarized for the safety, ITT, mITT, and PP populations. Individual subject demographics and baseline characteristics will be provided in listings.

8.4. Medical and Surgical History

Medical and surgical history will be coded using the MedDRA Version 18.0.

Subject medical and surgical history data including specific details will be presented in a listing.

8.5. Prior and Concurrent Medications

The number and percentages of all concomitant medications will be summarized by treatment group, Anatomical Therapeutic Chemical (ATC) level 4 and PT. The total number of concomitant medications and the number and percentages of subjects with at least 1 concomitant medication will be summarized by treatment group. All summaries will be performed using the safety population.

The number and percentages of all prior medications will be summarized similarly to concomitant medications in a separate table.

A concomitant medication is defined as any medication taken on or after the day of first dose of study drug. The prior medications are defined as any medication that starts and ends prior to the first dose of study drug.

8.6. Treatment Compliance

Dosing information, including date of administration, will be listed by subject.

9. EFFICACY ANALYSES

9.1. Primary Efficacy

9.1.1. Co-Primary Efficacy Endpoints

The co-primary efficacy endpoints include the following:

- Total Numeric-Transformed Modified Ashworth Score – Most Affected Limb (TNmAS - MAL)
- Clinical Global Impression of Change (CGIC)

9.1.2. Co-Primary Efficacy Analyses

The AERT 40 mg dose will be compared with placebo first (for both TNmAS-MAL and CGIC). If both comparisons are significant at the 0.05 level then the AERT 80 mg dose will be tested at the 0.05 level (both TNmAS-MAL and CGIC). Both co-primary efficacy endpoints need to meet the 0.05 level for the AERT 40 mg dose comparison with placebo for the study to be considered a success. Therefore, no adjustment for multiplicity is needed. The Day 84 comparison is the primary time point for both co-primary endpoints.

Descriptive statistics for each co-primary efficacy variable will be tabulated by study visit and treatment group. CGIC categories will also be summarized by frequencies and percentages by study visit and treatment group.

Note that if two or more limbs tie for Most Affected at baseline, then the Visit 5 (Day 84) scores for the tied limbs are assessed and the one with the worst score at Visit 5 becomes the Most Affected Limb in the primary analysis. In the case of a tie at baseline and at Visit 5, then both scores from Visit 4 and Visit 5 are summed for each limb and the highest (worst) total is flagged as the Most Affected Limb.

TNmAS-MAL will be analyzed using a restricted maximum likelihood (REML)-based mixed model for repeated measures (MMRM) with fixed effects for treatment, visit, study center, and the treatment-by-visit interaction; and with baseline score as a covariate. The outcome variable will be change from baseline scores. Study visit will be included in the model as a categorical variable (Visit 4 [Day 42] and Visit 5 [Day 84]) along with the treatment-by-visit interaction. Least squares means (LS means) will be used to compare treatments.

CGIC will also be analyzed using an REML-based MMRM with fixed effects for treatment, visit, study center, and the treatment-by-visit interaction. As the CGIC is a change score, no value is measured at baseline. The outcome variable will be CGIC scores. Study visit will be included in the model as a categorical variable (Visit 4 [Day 42] and Visit 5 [Day 84]) along with the treatment-by-visit interaction. LS means will be used to compare treatments.

For both models, pairwise treatment comparisons between the two AERT doses and placebo will be performed at each visit; however, the primary comparisons will be the contrasts between AERT 40 mg and placebo at Day 84. Unstructured covariance matrices will be utilized. If the model fails to converge with an unstructured covariance matrix other structures will be tried and the structure with the lowest corrected Akaike information criterion (AICC) will be used for the analysis. Full details will be included in the CSR. The Kenward Roger method will be used for computing the denominator degrees of freedom for the tests of fixed effects. Study centers may be pooled prior to unblinding.

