It is suggested that the testing of the upper limbs should take place while the subject is lying supine, with the upper limbs parallel to the trunk, elbows extended, wrists in a neutral position, and the lower limbs positioned parallel to one another. Exceptions are made for the shoulder extensors, where the arm should be moved from extension to 90 degrees of flexion, and for the shoulder internal rotators, where the arm should be moved from neutral to a maximum external rotation. For the lower limbs, it is recommended that the subject be lying on their side. Specifically for testing the soleus muscle, the hips and knees should be positioned in 45 degrees of flexion and the ankle is moved from maximum plantar flexion to maximum dorsiflexion. For the gastrocnemius muscle, hips should be in 45 degrees of flexion with the knees in maximum extension and the ankle is moved from maximum plantar flexion to maximum dorsiflexion. For the quadriceps femoris muscle, knees and hips should be in maximal extension and the knee is moved from maximum extension to maximum flexion. Throughout testing, the subject should be instructed to remain calm and relaxed, and when repeated testing is undertaken, testing should be initiated at the same time of the day to minimize possible changes in spasticity levels due to medication interaction.

To arrive at the TNmAS-MAL score, the total numerical score of a limb accounts for the sum of the 3 main joint muscular group scores. If two or more limbs tie for “Most Affected” at Visit 2 (Baseline), then the Visit 5 (Day 84) scores for the tied limbs will be assessed and the one with the worst score at Visit 5 will become the MAL in the primary analysis. In the case of a tie at Visit 2 (Baseline) and at Visit 5, then all of the scores from Visit 2 to Visit 5 will be summed and

the highest (worst) total will be flagged as the MAL. If a subject discontinues early, then the early termination visit scores will be used in place of the Visit 5 scores.

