The TNmAS-MAL assessment will always be performed by the study evaluator (someone other than the investigator) who has been appropriately trained to perform and assess the TNmAS-MAL, and when possible all TNmAS-MAL assessments should be performed for a particular subject by the same study evaluator throughout the study prior to any scheduled lab draw. The most affected limb will be determined by the study evaluator and the subject. The study evaluator must remain blinded to the subject's overall clinical, safety, and CGIC assessments.

The TNmAS-MAL assessment will be done at the visits specified in Table 1. The mAS and TNmAS-MAL are provided in Appendix 1.

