12.4 Withdrawal of Subjects

Withdrawn subjects are those who do not complete all evaluations and procedures outlined in the protocol. A subject will be considered to have discontinued prematurely if he/she withdraws after being randomized and prior to completing Visit 6 (Final Visit). Subjects who discontinue taking study drug for any reason for greater than 5 consecutive days must also be withdrawn from the study. Subjects may be withdrawn from the study because of any of the following:

- **Adverse Event:** An AE that, in the opinion of the Investigator or Sponsor, suggests that continued participation in the study is not in the subject's best interest for safety reasons (also see [Section 10](#)). All AEs that are present when the subject withdraws from the study will be followed as described in [Section 9.7.4](#).
- **Medical Condition:** Any medical condition that, in the Investigator's judgment, would increase the risk or interfere with the evaluation of study objectives.
- **Lost to Follow-up:** As per the comprehensive lost to follow-up guidance document that will be submitted to the IRB/IEC with the clinical protocol.
- **Subject Request:** Subject requests for any reason to be withdrawn or withdraws his/her consent.
- **Protocol Deviation:** A subject may be withdrawn from the study at the discretion of the Investigator or Sponsor due to poor compliance with protocol requirements that may compromise the study results or subject safety.
- **Enrollment in Another Study:** Enrollment in other protocols involving research drugs, medical devices, or surgeries.
- **Other Anti-spasticity Treatment:** Starting any other pharmacological anti-spasticity treatment during the study.

- **Relapse:** Subjects who experience an acute MS exacerbation/relapse (symptoms including but not limited to visual disturbance, dizziness, tingling, or extreme fatigue lasting greater than 24 hours and occurring at least 30 days after a previous relapse) requiring immediate therapy or adjustment in disease-modifying medication dose (eg, oral or intravenous high-dose steroid therapy). Upon resolution of symptoms, the subject may choose to be assessed for entry into the subsequent open-label extension study (Study OS440-3005).

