5.3. Analysis Variables

Variables to be analyzed include demographics and baseline characteristics, safety variables (adverse events, clinical laboratory investigations, vital signs, ECGs, USP questionnaire, and C-SSRS), and efficacy variables (TNmAS-MAL, CGIC, PGIC, EDSS, and TNmAS-TL). See Section 8 of the protocol for further details on the efficacy variables. Derived variables from study endpoints are described with the sections describing the analyses for these endpoints.

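### Ties for the most affected limb at baseline are broken by the Day 84 score, so the co-primary outcome chooses its own limb, and no sensitivity analysis varies the rule

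*SAP*

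**What the plan says.** SAP 9.1.2 resolves a baseline tie as follows: "the one with the worst score at Visit 5 becomes the Most Affected Limb in the primary analysis". Protocol 8.1 has the same rule: "the one with the worst score at Visit 5 will become the MAL in the primary analysis". If the limbs also tie at Visit 5, the SAP sums Visits 4 and 5 and the protocol sums Visits 2 to 5.

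SAP 9.1.2 makes Day 84 the primary time point and change from baseline the outcome. A limb score is the sum of three joints, each scored 0 to 5 (Protocol 8.1 and Appendix 1), so it is an integer from 0 to 15. Entry requires a score of only 2.

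For early leavers the protocol adds: "If a subject discontinues early, then the early termination visit scores will be used in place of the Visit 5 scores". SAP 9.1.2 does not repeat this step, although SAP 5.3 refers the reader on: "See Section 8 of the protocol for further details on the efficacy variables". SAP 7.3.3 has its own general rule for early termination data: "the early termination visit data will be analyzed at the closest scheduled visit", and "If the closest visit has valid data, the early termination data will be assigned to the next available visit".

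The sensitivity analyses in SAP 9.1.3 vary the population, centre interaction, visit averaging, handling of dropouts, missing-data assumptions and the arms included. None varies limb selection. TNmAS-Total Limbs uses the same MMRM (SAP 9.2.2) and needs no limb selection, but it is a secondary endpoint.

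**The concern.** An endpoint should not use its own value at the primary time point to decide what is measured. Here it does so for tied subjects only, so the co-primary mixes two quantities: change in a limb fixed before dosing, and the smallest improvement among limbs that were equally bad at baseline.

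The second quantity depends on how far limbs diverge by Day 84. If treatment alters that divergence, for example through the floor at 0, an effect proportional to the score, or a benefit that differs between limbs, the treatment contrast picks up a term unrelated to the mean effect. Study success needs both co-primaries for 40 mg, and 80 mg is tested only after that.

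**Working it through.** **Inputs.** From the documents: about 510 subjects, 3 × 170 (Protocol 5); limb scores 0-15; entry score at least 2. No tie rate, SD or between-limb correlation is available, so the following are assumptions: two competing limbs, baseline mean 6, SD 2.5, correlation 0.50-0.85. Day 84 score = baseline − 0.5 + subject noise (SD 1.5) + limb noise (SD 1.2 on placebo) + drug effect, rounded and clipped to the scale. There were 400,000 simulated subjects per arm. Negative change is improvement.

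**Ties.** 15.5%, 19.9% and 27.5% at correlations 0.50, 0.70 and 0.85. Of 170 per arm: 0.155 × 170 = 26 to 0.275 × 170 = 47.

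**Within-arm effect.** The expected maximum of two independent standard normals is 0.564. With equal baselines, taking the worse limb adds 0.564 × 1.2 = 0.68 point. Simulated: tied placebo subjects change by +0.19 instead of −0.47, a difference of 0.66.

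**Effect on the contrast.** The shift is approximately tie rate × 0.564 × (limb SD on drug − limb SD on placebo). It is zero when the spreads are equal. Simulated contrasts, plan rule vs mean of tied limbs:

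| Drug effect | Corr. 0.50 | Corr. 0.70 | Corr. 0.85 | Formula |
|---|---|---|---|---|
| Additive −0.8 | −0.790 vs −0.788 | −0.789 vs −0.786 | −0.788 vs −0.784 | 0 |
| Score scaled by 14.5% | −0.966 vs −0.951 | −0.946 vs −0.927 | −0.927 vs −0.901 | – |
| −0.8, limb SD 1.0 | −0.810 vs −0.792 | −0.814 vs −0.790 | −0.822 vs −0.789 | −0.017 to −0.031 |
| −0.8, limb SD 1.5 | −0.758 vs −0.780 | −0.748 vs −0.776 | −0.733 vs −0.773 | +0.026 to +0.047 |
| −0.8, limb SD 0.6 | −0.849 vs −0.798 | −0.865 vs −0.798 | −0.889 vs −0.797 | −0.052 to −0.093 |
| −0.8, limb SD 2.0 | −0.698 vs −0.760 | −0.674 vs −0.753 | −0.637 vs −0.746 | +0.070 to +0.124 |

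The additive case moves by under 1%, scaling by about 2-3%, SD 1.0 or 1.5 by about 2-5%, and SD 0.6 or 2.0 by about 6-15%. With no mean effect and only the spread changed, the rule adds 0.016-0.045 point (SD 1.0 or 1.5) or 0.05-0.12 point (SD 0.6 or 2.0). Under a strict null the shift is within 0.001.

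**Low baseline** (mean 3, SD 1.5, additive effect, no assumed change in SD): ties 24-41%; contrasts −0.734 vs −0.720, −0.736 vs −0.719 and −0.733 vs −0.710, about 2-3% larger because of the floor.

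**Scale.** With SD 1.91 in both arms, SE = 1.91 × √(2/170) = 0.21; across scenarios 0.19-0.24. The largest shift in the mean-6 runs is about 0.12/0.24 = 0.5 SE.

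**A second, four-limb model** (baseline SD 3, correlation 0.5-0.95) compared the rule with a random choice among tied limbs. Ties were 16-39%. Type I error with identical arms was 0.051 under the rule and 0.049 with random choice. A uniform 1-point benefit gave the same contrast within 0.01. For a 0.6-point benefit that varies between limbs, power was 0.85 vs 0.91 (between-limb SD 1) and 0.46 vs 0.71 (SD 2). A 15% effect applied to baseline only, leaving the noise unscaled, gave almost no shift, so the proportional result depends on its form.

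**Early leavers.** The midpoint of Days 42 and 84 is Day 63.
- Visit 4 done, leaves on Days 43-83: SAP 7.3.3 sends the data to Visit 5, so the documents agree.
- No Visit 4 score, leaves by Day 62: the data go to Visit 4 (or to Visit 3 up to Day 25, if that visit counts), so SAP 9.1.2 has no Visit 5 score to break the tie. Day 63 is equidistant.
- Visit 5 done, leaves on Days 85-91: Protocol 12.4 counts this as premature discontinuation, so Protocol 8.1 read literally replaces an existing Visit 5 score when choosing the limb. The SAP keeps Visit 5.
- Visit 4 done but no Visit 5 or early termination score: no limb is defined in either document.

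The two second-level rules rank limbs identically: Visit 2 is tied and Visit 3 has no TNmAS.

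**The case against.** The rule is prespecified, identical in every arm and applied to a tie status fixed before dosing. It gives a definable endpoint, the worst Day 84 score among equally bad limbs, and it withholds credit when one of them stays bad. A uniform effect moves the contrast by 0.002-0.004 point. The larger shifts need large assumed changes in spread, and where benefit differs between limbs the distortion runs against the drug. All of this stands, and it is why the point is not graded higher.

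Three further limits also stand. The simulations compare raw Day 84 changes, without Visit 4, the MMRM, centre effects or dropout. Limbs still tied at Day 84 give the same value whichever is chosen, so only 12-21% (about 20-36 per arm) are tied and discordant on placebo. TNmAS-Total Limbs shows whether the overall result depends on choosing a limb at all, though it does not isolate the tie rule.

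On early termination, SAP 5.3 points to Protocol Section 8 and SAP 5.1 defers to the protocol. The omission is therefore silence and not a contradiction, and reading Protocol 8.1 as overwriting an observed Visit 5 score is strained. These are minor gaps. None of this supplies a reason to let the outcome choose the limb when an outcome-independent rule uses data already collected.

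**Conclusion.** The concern holds and should be fixed before unblinding. For tied subjects the co-primary outcome selects its own limb, and no planned analysis shows whether that matters. It is not a type I error problem under a strict null, nor evidence of bias towards the drug.

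The firm result is within-arm: tied subjects look about two-thirds of a point worse under the first model. The effect on the contrast depends on a differential spread between limbs that nobody can know in advance: under 1% for a uniform effect away from the floor, a few per cent for moderate changes in spread or a low baseline, and about 6-15% for large ones. The existence of the rule is certain; its size in this trial is unknown, because tie rate, SD and correlation are all assumed.

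**What to change.** Before unblinding, change SAP 9.1.2 so that no post-baseline score selects the limb.

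- **Preferred:** for limbs tied at Visit 2, analyse the mean change of the tied limbs. Their baseline is the same, so the covariate is unchanged, and all limbs are already scored for TNmAS-Total Limbs.
- **If a single limb must be kept:** use the limb named at Visit 2, if that was recorded before dosing, otherwise a fixed or random order. Protocol 8.1 says "The most affected limb will be determined by the study evaluator and the subject", while Protocol 6 and Table 1 name the evaluator alone; reconcile these first. The Visit 1 score is a poor first tie-break because it precedes anti-spasticity washout.

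Keep the Day 84 rule as a sensitivity analysis in SAP 9.1.3, report tied subjects per arm, list the change in SAP 3.3 and align Protocol 8.1. Either option also closes the early-leaver and undefined-limb gaps.

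The cost is one derivation rule, three SAP edits and a protocol amendment needing Sponsor and IRB/IEC approval (Protocol 12.2). Averaging needs no new data but slightly changes the estimand and gives non-integer scores for tied subjects; the simulated placebo SD of change falls from 1.91-1.92 to 1.86-1.89. A fixed-order limb leaves it at 1.91-1.92.

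**Fallback without an amendment:** add the outcome-independent version to SAP 9.1.3, write the early termination step into SAP 9.1.2, and report tie counts by arm.
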